2. SYNOPSIS

Study Title	Neuroimaging Approaches to Deconstructing Acupuncture for Chronic Pain
Study Sponsor	National Institutes of Health, National Center for Complementary and Alternative Medicine Grant Number: R01AT007550
Study Objective	To evaluate the impact of acupuncture-induced somatosensory afference on altered neurobiology and analgesia in FM.
Study Design	This study design has two components: 1) a cross sectional assessment of brain chemistry, connectivity and response to pain in healthy controls and age- and sex-matched fibromyalgia patients, and 2) a longitudinal assessment of the same fibromyalgia patients randomized to either electro-acupuncture (EA) or mock laser acupuncture (ML).
Study Interventions	Electro acupuncture and mock laser acupuncture. Treatments will be delivered at 2x/week for 4 weeks, for a total of 8 treatments.
Study Duration	The study duration for healthy controls will be 1 week, with a 4 week screening window. The study duration for fibromyalgia patients will be up to 10 weeks: 4- week screening window prior to baseline; 1-week of baseline, 4 week treatment period, and 1 week of follow up.
Sample Size and Population	We will evaluate 40 healthy controls and 80 fibromyalgia patients (n=40 EA and n=40 ML). Demographics will be representative of the population of southeastern Michigan.

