Changes in connectivity z-score for a typical connectivity biomarker are expected to follow a different slope in FM vs. HC patients in response to pressure pain. Based on our previous studies we expect the slope of 1.3 vs. 0.8 (FM vs. HC, respectively) with the standard deviation of the pain score of approximately 1 and standard deviation of the connectivity score at a given level of pressure pain of around 0.5. This ensures we will have over 86% power to detect a difference in connectivity responses to evoked pain.

ROC Analysis

In order to characterize the potential of biomarkers to predict the disease, a decision rule predicting FM status, a binary outcome, based on connectivity, Glx/GABA and evoked pain biomarkers. Our primary method for rule development will be logistic regression. Stepwise variable selection procedures using Likelihood Ratio tests and Akaike Information Criterion (AIC) will be performed to identify the set of significant predictors. A cutpoint on the linear predictor in the logistic model will define the decision rule with values above the cutpoint for a particular subject interpreted as prediction of treatment success for the subject. A set of rules obtained by varying the cutpoint will be summarized by the Receiver-Operating-Characteristic (ROC) curve plotting sensitivity by 1-specificity of the rule. The area under the ROC for the model will characterize the quality of prediction. The area under the ROC will serve as the overall measure of discriminative ability of the model. In order to obtain a realistic estimate of ROC, cross-validation will be used when estimating sensitivity and specificity corresponding to various cutoff values.

The assessment of power is based on a test for area under the ROC. We hypothesize that an area of 0.7 can be achieved. A test for area <0.6 vs. >0.6 shows that we will have 83% power to discriminate area of 0.7 from 0.6 or less with 80 FM patients and 20 controls, using a two-sided test at the significance level of 0.05. This indicates that we will have the precision of at least 0.1 on the area under ROC scale.

11.2. Aim 2: Evaluate longitudinal desensitization effects of electro- and mock laser acupuncture interventions on the neurocircuitry underlying chronic pain in FM, correlate the change in pain with changes in neurocircuitry physiology, study neuroimaging biomarkers as mediators for the treatment effect.

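### The ROC analysis does not place stepwise biomarker selection inside the cross-validation, so the reported AUC may be too high when signals are weak

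*Combined protocol and SAP*

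**What the plan says.** The ROC paragraph of section 11.1 (Aim 1) develops a logistic rule for fibromyalgia (FM) status, "based on connectivity, Glx/GABA and evoked pain biomarkers". Its steps come in this order:

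1. Selection: "Stepwise variable selection procedures using Likelihood Ratio tests and Akaike Information Criterion (AIC) will be performed to identify the set of significant predictors".
2. A cutpoint on the linear predictor of that model, varied to trace the ROC curve, with the area as the overall measure of discrimination.
3. Cross-validation: "In order to obtain a realistic estimate of ROC", the plan says that "cross-validation will be used when estimating sensitivity and specificity corresponding to various cutoff values".
4. Power: "We hypothesize that an area of 0.7 can be achieved", and "A test for area <0.6 vs. >0.6 shows that we will have 83% power" to tell 0.7 from 0.6 or less, "with 80 FM patients and 20 controls, using a two-sided test at the significance level of 0.05".

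The paragraph does not give the number of candidate biomarkers, the entry or removal level, the number of folds, or whether selection is repeated in each fold. No other section supplies these.

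**The concern.** Cross-validation gives an honest AUC only if the held-out subjects played no part in building the rule they are scored on. The text identifies one set of predictors and then mentions cross-validation. An analyst who follows that order selects on everyone, refits only the coefficients in each fold, and scores held-out subjects on predictors that their own data helped to choose.

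Choice of brain region could add to this. Sections 9.3.1 and 9.3.3 produce FM-versus-control difference maps. If clusters found there become ROC candidates, group status is used once more outside the folds. The plan does not say that this will happen, and does not exclude it.

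The AUC is the plan's summary of how well the biomarkers identify FM, and the improvement it hopes to show is 0.7 - 0.6 = 0.1. Optimism of several hundredths is a large share of that.

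**Working it through.** **The plan's own figure.** Hanley-McNeil standard error, with n1 = 80 patients and n2 = 20 controls:

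SE(A)² = [A(1-A) + (n1-1)(Q1-A²) + (n2-1)(Q2-A²)] / (n1·n2), where Q1 = A/(2-A) and Q2 = 2A²/(1+A).

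This gives SE(0.5) = 0.0725, SE(0.6) = 0.0679 and SE(0.7) = 0.0596. Power = Φ[(A1 - A0 - 1.96·SE(A0)) / SE(A1)].

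- Against 0.6: (0.1 - 0.1331)/0.0596 = -0.555, power 29%.
- Against 0.5: (0.2 - 0.1421)/0.0596 = 0.971, power 83%.

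The stated 83% therefore fits a null of 0.5, not the stated 0.6. It also uses 20 controls, where the synopsis says "We will evaluate 40 healthy controls and 80 fibromyalgia patients"; with 40 controls, power against 0.6 is 46%. These are separate matters, but they show which standard errors apply below.

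**Candidate count (assumed).** Two networks (9.3.1), two voxels times Glx and GABA (9.3.2) and two evoked-pain contrasts (9.3.3) give 2 + 4 + 2 = 8. If the metabolites enter as a ratio per voxel, it is 2 + 2 + 2 = 6. The main range used is 6-10.

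**Why selection matters.** With one degree of freedom, AIC admits a predictor when its likelihood-ratio (LR) statistic exceeds 2, which a useless biomarker does with probability 0.157. At least one of 10 independent useless biomarkers enters with probability 1 - 0.843^10 = 0.82 (simulated 0.84). With a 5% LR rule it is 1 - 0.95^10 = 0.40 (simulated 0.39).

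**Simulation.** Independent normal biomarkers with no group difference, bidirectional stepwise logistic regression, stratified 10-fold cross-validation, 200-1000 datasets per cell. The AUC counts as 0.5 when selection on all subjects chooses nothing. Mean cross-validated AUC (true value 0.50), 80 patients and 40 controls, selection once on all subjects:

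| Candidates | AIC | 5% LR rule |
|---|---|---|
| 3 | 0.54 | 0.52 |
| 8 | 0.58 | 0.55 |
| 10 | 0.59 | 0.55 |
| 20 | 0.64 | 0.60 |

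With 6 candidates under AIC the mean is 0.56. Repeat runs gave 0.57 for 6 candidates and 0.58-0.59 for 8 under AIC, and 0.54 for 8 under the LR rule. With selection repeated inside every fold the mean is 0.48-0.50 in all settings. With 20 controls, AIC gives 0.58, 0.61 and 0.62 for 6, 8 and 10 candidates. Correlation of 0.4 among 10 candidates (40 controls, AIC) leaves 0.58.

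**Formal test against 0.6, all biomarkers null.** Upward rejection under AIC is 0.2% (6 candidates) and 1.0% (10) with 40 controls, and 0.9% and 4.1% with 20. The nominal upper tail is 2.5%.

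**With real signal (80 and 40, AIC).**

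- One biomarker of AUC 0.60 with 6, 8 or 12 candidates: mean 0.61, 0.61 and 0.63, against 0.55, 0.54 and 0.54 nested. Upward rejection of 0.6 was 5-14% over two runs, against 2-4% nested.
- One biomarker of AUC 0.70 and seven null: 0.71 against 0.67-0.68 nested, a gap of 0.03-0.04.
- Effects as assumed in section 11.1: connectivity (1 - 0.5)/0.5 = 1.0 and Glx (11.5 - 10.5)/1.4 = 0.71. Two biomarkers at 1.0, two at 0.71 (GABA assumed similar to Glx) and four null: 0.876 against 0.861 nested and 0.874 in new subjects. The gaps are 0.015 and 0.002, so of the order of 0.01.

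**The case against.** The strongest reply is that the text never says selection uses all subjects. Sensitivity and specificity over all cutoffs are the ROC curve, so the performance estimate itself is cross-validated, not just the choice of a cutoff. Rule development includes selection, and cross-validating the whole rule is a permissible reading with no optimism. This stands: a reader might infer that the plan commits to selecting on everyone and validates cutoffs alone, but the documents do not say so. What remains is that they do not exclude it, and the order of the text leads there.

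A second tempting inference is that useless biomarkers will reach the plan's 0.6 benchmark. That depends on an unstated candidate count and on AIC rather than a strict LR rule, and the plan names both criteria. A point estimate above 0.6 is also not the plan's test, which null biomarkers seldom pass.

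Third, the plan expects strong effects, for which the bias is negligible. That is correct if those effects hold. The plan's own ROC hypothesis of 0.7 is much weaker than the roughly 0.87 those effects imply in the simulation, and near 0.7 the bias is 0.03-0.04.

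Finally, the ROC is descriptive support for Aim 1. It does not enter the randomised comparison or the interim decisions. This limits the severity.

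**Conclusion.** The concern holds in conditional form: the plan does not place selection inside the folds, and if it is done once beforehand the cross-validated AUC is optimistic. With 80 patients and 40 controls the excess is about 0.06-0.09 for useless biomarkers under AIC with 6-10 candidates (0.56-0.59 against 0.50), about 0.03-0.05 under a 5% LR rule, 0.03-0.04 with one biomarker of AUC 0.70 among eight, and about 0.01 under the effects assumed in section 11.1. These figures rest on an assumed candidate count, normal and mostly independent biomarkers, and ten folds. The main consequence is an inflated AUC when signals are weak. The test against 0.6 is inflated when a weak biomarker near that value exists, and only rarely misled when all are null. This should be fixed before analysis; it does not threaten the trial's main comparisons.

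**What to change.** State in section 11.1 that the whole rule-building step is repeated within every training fold: stepwise selection, coefficient fitting, and any choice of region or cluster that uses FM or control status. Report, and test against the benchmark, only the resulting nested cross-validated AUC. In the same sentence or two, list the candidate biomarkers and fix the selection criterion, its entry and removal levels, and the number of folds.

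The cost is a short change of wording and a few lines of code; no data collection changes. The downside is that the reported AUC may be lower. If nested selection is already intended, the sentence simply confirms it.

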7. STUDY DESIGN

7.1. Overall Design

Our overall goal is to understand the role somatosensation plays in modulating analgesia and neuroimaging markers related to altered neural processing of pain in FM (Table 1; Figure 2). Eighty (80) FM women patients will be evaluated with MRI at baseline and after acupuncture treatment (electro-acupuncture, EA; mock laser acupuncture, ML; n=40 per group). Treatments will be delivered at 2x/week for 4 weeks, for a total of 8 treatments. An additional 40 healthy age-matched adult women will serve as a control for neuroimaging markers collected from baseline FM patients, and will allow us to assess central pain pathology in our population (Aim 1). The HCs will not be treated with acupuncture since the goal of this investigation is to investigate potential mechanisms for acupuncture in chronic pain patients. In addition to our neuroimaging outcomes, we will also assess clinical and experimental pain outcomes during the study period from all subjects. These data in combination with other outcomes will be used to perform secondary analyses.

Table 1 – Neuroimaging Outcomes

Outcome	fMRI Protocol	Rationale
Clinical Pain	- resting fcMRI and ¹ H-MRS	Neuroimaging markers for clinical pain directly reflect our primary clinical outcome. Markers are needed for localized brain neurochemistry and associated network connectivity and their relation to clinical pain.
Experimental Pain	- fMRI with pressure pain and conditioned pain modulation.	Protocols for brain response to experimental pain are more mature than for clinical pain (facilitating comparison to prior research) and allow the assessment of hyperalgesia and allodynia.

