11. STATISTICAL CONSIDERATIONS

11.1. Aim 1: At baseline, characterize altered somatosensory neurocircuitry underlying chronic pain in FM.

Hypothesis 1: Using resting fcMRI, the insula in FM patients will show more correlation with DMN, and more anti-correlation with SMN, compared to HC.

We will use dual-regression independent component analysis (ICA) to evaluate resting connectivity between DMN/SMN and insula. Two-sample t-tests will compare FM vs. HC, cluster-corrected at $p=0.05$.

Based on our previous studies, assuming DMN connectivity z score (middle insula region) of 1 for a fibromyalgia patient vs. 0.5 for a healthy control with a common standard deviation of 0.5, we will expect a typical relative effect of 1 (mean ICA-derived z score over its standard deviation). Similar effects (negative connectivity values) are expected for SMN-derived biomarkers. With the planned numbers of subjects we will have the power exceeding 97% to detect the effects by a two-sided t-test.

Hypothesis 2: Using $^1\text{H-MRS}$, FM patients will show pain related increased Glx and reduced levels of GABA within the insula and S2 as compared to HC.

Metabolite concentration from regions of interest will be assessed using spectra data input into LCModel. A two-sample T-test will compare FM vs. HC, significant at $p=0.05$.

Our sample size calculation for difference between FM and HC assumes (from pilot data) that Glx, a proxy for glutamate concentration, has mean(SD) = 10.5(1.4) in arbitrary institutional units (AIU) and a FM-HC relative difference in excess of 10%. Thus we conservatively hypothesize an average Glx around 11.5 AIU and GABA around 1.3 mmol/kg in the FM group. We conclude that we will have the power of at least 84% for the GABA and 81% for the Glx based on a two-sided t-test with unequal N (80 in FM vs. 20 in HC) at the significance level of 0.05.

Hypothesis 3: Using evoked pain fMRI, FM patients will be more sensitive to evoked pressure pain and demonstrate greater insula activation to pain stimuli, compared to HC.

A general linear model will assess brain response to experimental pain from a block design BOLD fMRI run. A group level FM - HC difference map will use a two sample t-test, cluster corrected at $p=0.05$.

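### The stated 83% power to separate an AUC of 0.7 from 0.6 does not follow from its inputs: it is about 26–39% with the 20 controls stated and 42–55% with the 40 planned

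*Combined protocol and SAP*

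**What the plan says.** Section 11.1 (Aim 1), under ROC Analysis, describes a logistic-regression rule that classifies participants as FM or healthy control from the imaging biomarkers. Predictors are chosen stepwise, and the rule is judged by its area under the ROC curve. The target is given as "We hypothesize that an area of 0.7 can be achieved". The test sets areas below 0.6 against areas above it, and the power statement is that "we will have 83% power to discriminate area of 0.7 from 0.6 or less with 80 FM patients and 20 controls", with a two-sided test at 0.05. The plan then concludes: "This indicates that we will have the precision of at least 0.1 on the area under ROC scale".

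The count of 20 controls also appears in the spectroscopy power statement for Hypothesis 2 of the same section: "based on a two-sided t-test with unequal N (80 in FM vs. 20 in HC) at the significance level of 0.05". The design differs. Section 7.1 says "An additional 40 healthy age-matched adult women will serve as a control", and the synopsis likewise gives 40 healthy controls with 80 FM patients.

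**The concern.** Two things stand out. First, an AUC estimated from 80 and 20 subjects has a standard error of roughly 0.06 to 0.07, so a difference of 0.1 is only about one and a half standard errors. Power of 83% at two-sided 0.05 needs nearly three. Second, the control count is half of what the design enrols, so the figure might merely be out of date and conservative. It therefore has to be checked at both sample sizes.

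At stake is how a null result would be read. The plan presents the FM-versus-control rule as well powered to show an AUC above 0.6. If the real power is near one half or less, a non-significant result says little about whether the biomarkers discriminate, yet a reader who trusts 83% could take it as evidence that they do not.

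**Working it through.** **Inputs.** From Section 11.1, ROC Analysis: alternative AUC 0.7, null AUC 0.6, 80 FM, 20 controls, two-sided 0.05. From the synopsis and Section 7.1: 40 controls. Not stated, so assumed here: the variance formula, independent subjects, a fixed score, and no loss of scans.

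**Formula.** Hanley–McNeil, for AUC *A* with n₁ FM and n₀ controls:

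SE² = [A(1−A) + (n₁−1)(Q₁−A²) + (n₀−1)(Q₂−A²)] / (n₁n₀), with Q₁ = A/(2−A) and Q₂ = 2A²/(1+A).

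Power = Φ((A₁ − A₀ − 1.96·SE₀)/SE₁), with SE₀ at the null and SE₁ at the alternative.

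**Trying to reproduce 83% at 80/20.**
- At 0.7: Q₁ = 0.5385, Q₂ = 0.5765. SE₁² = (0.21 + 79×0.0485 + 19×0.0865)/1600 = 0.00355, so SE₁ = 0.0596.
- At 0.6: Q₁ = 0.4286, Q₂ = 0.45. SE₀² = (0.24 + 79×0.0686 + 19×0.09)/1600 = 0.00460, so SE₀ = 0.0679.
- Power = Φ((0.1 − 1.96×0.0679)/0.0596) = Φ(−0.55) = **29.0%**.

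**At 80/40.** SE₁ = 0.0481 and SE₀ = 0.0535. Power = Φ((0.1 − 1.96×0.0535)/0.0481) = Φ(−0.10) = **45.9%**.

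**Other versions, null 0.6, two-sided 0.05:**

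| Version | 80/20 | 80/40 |
|---|---|---|
| Hanley–McNeil, both SEs | 29.0% | 45.9% |
| Hanley–McNeil, SE at 0.7 only | 38.9% | 54.7% |
| Hanley–McNeil, group roles swapped, both SEs | 26.6% | 42.7% |
| Obuchowski binormal, both SEs | 29.3% | 45.8% |
| Obuchowski binormal, SE at 0.7 only | 33.7% | 49.8% |
| Lowest of 20 analytic versions (swapped, logit scale) | 26.0% | 41.9% |
| Simulation, DeLong-type SE, raw scale | 36.0% | 51.2% |
| Simulation, DeLong-type SE, logit scale | 28.5% | 45.2% |

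A one-sided test at 0.05 reaches at most 51% (80/20) and 67% (80/40) by Hanley–McNeil.

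**How far off.** For 83% power the SE would have to be about 0.1/(1.96 + 0.954) = 0.034. With both SEs in Hanley–McNeil, that takes about 182 FM and 91 controls at 2:1. With FM held at 80, it takes more than 900 controls.

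**A possible origin.** With a null of 0.5 at 80/20, SE₀ = 0.0725, and power = Φ((0.2 − 1.96×0.0725)/0.0596) = Φ(0.97) = 83.4%. Obuchowski gives 83.0%. Other versions run from 71% to 92%, so the match depends on the formula.

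**Precision.** The 95% half-width at AUC 0.7 is 1.96×0.0596 = 0.117 with 20 controls and 1.96×0.0481 = 0.094 with 40. Across formulas it is 0.12–0.14 and 0.09–0.10.

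**The other use of 20 controls.** For Glx (10.5 against 11.5, SD 1.4), a two-sample noncentral t calculation gives 80.8% at 80/20, which reproduces the stated 81%, and 95.5% at 80/40. That statement is a valid lower bound with an inconsistent N.

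**The case against.** The strongest objection is that the plan gives no variance formula or score distribution, so the recomputed range rests on assumptions. That is right, and the range should be read accordingly. Less usual choices go somewhat beyond it: a simulated Wald test with the Hanley–McNeil SE gives 42.9% at 80/20, and strongly unequal binormal variances give up to about 53% at 80/20 and 58% at 80/40. None of these is close to 83%. A paired comparison of two highly correlated AUCs could pass through 83%, but that is not the test described.

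The precision sentence can fairly be read as a detectable difference and not as a confidence half-width. On that reading it fails together with the power. Read as a half-width, it is roughly true at 40 controls, although not for the reason given.

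The null of 0.5 as origin is an inference, and nothing below depends on it. The consequence is also limited: the ROC rule is not among the three numbered hypotheses or the synopsis analyses, and nothing in the documents shows that this figure set the sample size.

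**Conclusion.** The power statement is wrong as written. Against a null AUC of 0.6, true power at AUC 0.7 is about 26–39% with the stated 20 controls and 42–55% with the planned 40. The out-of-date control count does not explain the gap, because the claim fails at both sizes. At the plan's own hypothesised AUC, the test would miss more often than not at 80/20 and about half the time at 80/40.

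These figures assume a single AUC from a fixed score, independent subjects and no missing scans. The planned stepwise selection, and the fact that "cross-validation will be used when estimating sensitivity and specificity corresponding to various cutoff values", add uncertainty that is not counted here. The error should be corrected, but it affects only a supporting Aim 1 analysis.

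**What to change.** In Section 11.1, ROC Analysis, keep the 0.6 null and restate the power for 80 FM and 40 controls with one named formula. Using Hanley–McNeil with the SE at both null and alternative, that is 45.9% for a true AUC of 0.7 and Φ((0.15 − 1.96×0.0535)/0.0443) = 84.6% for a true AUC of 0.75; 80% power needs a true AUC of about 0.74. Say that predictor selection and cross-validation are not allowed for.

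Replace the precision sentence with a 95% half-width of about 0.09–0.10 at AUC 0.7 with 40 controls, or delete it.

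If a null of 0.5 was intended, say so and give its power at 80/40 (96.9% by the same formula). Acknowledge that showing an AUC above 0.5 is a weaker claim than the one now written; that is a change of hypothesis, not a text correction.

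For consistency, change 20 to 40 controls in the spectroscopy power statement (Glx about 95.5%). GABA cannot be recomputed, because no control mean or SD is given.

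With the 0.6 null kept, the cost is a text edit. Enrolment, data and analysis stay as they are, and one stated power becomes less favourable.

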9.3.1. Functional connectivity MRI

Resting 6min scans, performed with subjects resting comfortably in the scanner with eyes open, will be completed at the beginning of the scan session. In order to quantify intrinsic brain connectivity, functional MRI data will be analyzed with both a dual-regression ICA approach and seed-voxel approach. These approaches are complementary, as they quantify intrinsic brain connectivity on a network level (dual regression pICA) and a more specific region-focused level (seed-voxel). Physiological data will also be collected simultaneously to the fcMRI data, as cardio-respiratory fluctuations are known to influence fMRI intrinsic connectivity estimation within several brain networks [95, 96]. A similar approach will be used to evaluate the sustained cuff pain 6min scan.

Dual Regression ICA Approach: The within- and between-subject resting fMRI data analysis will be performed using ICA through Multivariate Exploratory Linear Optimized Decomposition into Independent Components (MELODIC, an FSL tool) and a previously validated dual regression approach [97]. This technique allows for voxel-wise comparisons of resting state functional connectivity by first temporally concatenating resting fMRI data from all subjects, followed by back-reconstructing the group networks for individual subjects, which are then used for within- and between-subject group and difference maps. This technique does not regress out global signal (enhancing interpretation of anti-correlations), and has been found to have moderate to high test-retest reliability in previous studies [98]. This process will be completed for networks of interest (DMN, SMN). The MVN will also be evaluated as a control network. Group analyses will be performed to evaluate intrinsic brain connectivity differences between FM and HC groups, how this intrinsic connectivity covaries with spontaneous pain intensity in FM patients, and how networks differentially change following EA and ML. The results will be threshold at $p < 0.05$, cluster-corrected for multiple comparisons.

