This aim evaluates a *mechanistic* value of the neuroimaging biomarkers by studying their response to treatment and correlation between the change in biomarker measurements and changes in pain induced by treatments, and biomarker mediation effects.

Hypothesis 1: EA, which involves greater somatosensory afference, will more readily reduce resting insula connectivity to SMN and DMN compared to ML. The change in pain will correlate with change in insula connectivity for EA, but not ML. Insula connectivity will represent a mediator for the treatment effect.

Treatment effects on connectivity

We will perform dual-regression ICA with group level estimates for baseline and post-treatment fcMRI data (DMN and SMN) entered into a linear mixed model with factors STIM (levels EA, ML) and TIME (levels baseline and post-therapy). Time by treatment interaction effect will be of main interest in the analysis. If a significant main effect or interaction is found, we will perform post-hoc difference map analyses, to evaluate which group produced the greatest change in resting connectivity.

Power analysis for fcMRI is based on data from the preliminary study on intrinsic connectivity and its short-term response to acupuncture. From preliminary data on 15 subjects, we estimate the SD of the number of voxels activated before and after acupuncture in the default mode independent component to be 2860 and 4559, respectively. The covariance between these before and after counts is 3388878. This implies the standard deviation of the within-subject change in connectivity of $\sqrt{2860^2+4559^2-2*3388878}=4710$. Based on the same data, we find the before and after means to be 7078 and 9844, respectively. Then, a two-sided paired t-test for the presence of change will have the effect size of 0.6 and the power of 95% with 40 patients in the EA group.

Based the similar mean connectivity difference of around 3000 between ML and EA, and the same SD of 4710 we will have 80% power to detect the difference between treatments with respect to the mean within-patient change in connectivity.

Correlation with pain

A linear mixed model will be used to regress BPI pain measurements on the neuro-imaging biomarkers. Correlation between clinical pain and biomarkers is the primary target.

We hypothesize a correlation coefficient of at least 0.5 between pain and connectivity z score in the EA arm. This will give us 94% power to detect the correlation.

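### A main effect alone can open the maps meant to say which arm changed most, although only the TIME-by-STIM interaction is evidence on that question

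*Combined protocol and SAP*

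**What the plan says.** In Section 11.2, Aim 2, Hypothesis 1 (treatment effects on connectivity), group-level estimates for DMN and SMN are "entered into a linear mixed model with factors STIM (levels EA, ML) and TIME (levels baseline and post-therapy"). The plan then names its target: "Time by treatment interaction effect will be of main interest in the analysis". The next sentence sets the rule for follow-up: "If a significant main effect or interaction is found, we will perform post-hoc difference map analyses", and gives the purpose of those maps as "to evaluate which group produced the greatest change in resting connectivity".

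The section does not say what contrast a post-hoc difference map contains, and it gives no alpha for the tests that open the step. Section 9.3.1 gives the threshold for connectivity maps: "The results will be threshold at $p < 0.05$, cluster-corrected for multiple comparisons".

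Other sections point two ways on the contrast:

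- **Between groups.** Section 11.1 (Hypothesis 3) uses the term difference map for a two-sample FM-HC comparison. Section 11.3 (Hypothesis 1) uses it for a comparison of therapies.
- **Within arm.** Section 11.2, Hypothesis 3 follows its mixed model with post-hoc paired t-tests and says this resembles the connectivity approach. Hypothesis 2 also pairs mixed models with paired t-tests.

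**The concern.** The trigger and the purpose do not match. The follow-up step is meant to rank the arms on change, yet it can be opened by results that carry no information on that ranking. If both arms change by the same amount, TIME is significant, the interaction is null, and the rule still sends the analyst on to ask which arm changed more.

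A shared change is plausible here. Sections 6.2.4 and 9.3.1 report that DMN-insula connectivity fell after both manual and sham acupuncture in earlier work (a sham with somatosensation, so not the same as ML). The Glx power calculation in Section 11.2 also expects a fall in both arms, 1.5 against about 1 AIU.

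At stake is the trial's mechanistic claim. Section 5 words the connectivity hypothesis as a reduction under EA and none under ML. A significant pre-post map in EA beside a non-significant one in ML would look like confirmation, even with no difference in true change.

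**Working it through.** **1. Reproduce the plan's figures.** The inputs are in Section 11.2: SDs before and after acupuncture "to be 2860 and 4559, respectively"; "The covariance between these before and after counts is 3388878"; "we find the before and after means to be 7078 and 9844, respectively". The Synopsis gives 40 patients per arm.

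- SD of change = √(2860² + 4559² − 2 × 3388878) = 4710, as stated.
- Standardised change = (9844 − 7078)/4710 = 2766/4710 = 0.587, which the plan rounds to 0.6.
- Paired t-test, n = 40: power 95.2% at 0.587 and 95.9% at 0.6 (stated 95%).
- Between-arm difference in change of 3000, SD 4710, 40 per arm: power 80.3% by the noncentral t with 78 df, 81.3% by the normal approximation (stated 80%).

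The stated powers reproduce and are not in question.

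**2. What each effect measures.** Write the 2 × 2 model so that mean change in ML is b and mean change in EA is b + c.

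- Interaction: (b + c) − b = c, the difference in change.
- TIME main effect: the average change, b + c/2. With equal change (c = 0) it equals b, so it is non-zero whenever both arms move together.
- STIM main effect: the arm difference averaged over both visits. A baseline imbalance alone can produce it.

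**3. How often the written trigger opens without a difference in change.** Each test is taken at an assumed two-sided 0.05.

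- With no effects at all, three independent tests give 1 − 0.95³ = 14.3% (13.5% simulated).
- With an equal true change of 2766 voxels in both arms, the trigger opens in 99.9% of simulated trials. In 95.0% it opens on a main effect with a non-significant interaction.

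**4. Consequence if the maps are between-arm contrasts of change.** That contrast is c. With complete data in a 2 × 2 design its test is the interaction test itself. In simulation with equal true change it is significant in about 5% of trials at every size of change, and the loose trigger adds nothing.

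**5. Consequence if the maps are within-arm pre-post tests compared by significance.** Both arms have the same true standardised change, with 40 per arm and one summary measure. The last two columns are joint probabilities over all trials.

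| Common change | TIME significant | TIME and exactly one arm significant | Interaction and exactly one arm significant |
|---|---|---|---|
| 0.2 | about 43% | about 27% | about 4.5% |
| 0.3 | about 75% | about 45% | about 4.8% |
| 0.4 | about 94% | about 41% | about 4.4% |
| 0.587 (pilot) | 99.9% | about 9% | about 2.1% |

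By symmetry, about half of each figure in the third column favours EA.

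The last row can be checked by hand. Each arm has 95.2% power, so exactly one is significant with probability 2 × 0.952 × 0.048 = 0.091, and TIME is almost always significant.

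A separate simulation used the document's own SDs and covariance and the full trigger (TIME, STIM or interaction). It gives 33% at a common change of 1000 voxels, 47% at 1500, 37% at 2000 and 9.1% at 2766. With an interaction-only trigger the figures are 4.6%, 4.9%, 4.4% and 2.1%.

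**The case against.** The strongest reply is that a difference map is a between-group contrast. Sections 11.1 and 11.3 use the term that way, Section 9.3.1 speaks of differential change after EA and ML at a corrected threshold, and Section 11.2 powers the between-treatment difference in change. On that reading the map repeats the interaction and no error rate is inflated. This stands, and it rules out a general claim that the trigger inflates the false-positive rate of the EA-ML comparison.

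It does not settle the matter. On that reading the follow-up adds nothing to the interaction, whereas Hypotheses 2 and 3 in the same section describe paired tests. The within-arm reading therefore remains open and is arguably the more natural one.

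A second reply is that the plan nowhere says one significant and one non-significant arm will count as evidence of a difference. That is also correct. A reader might infer such a rule from the EA-reduces, ML-does-not wording, but the documents do not state it. The phrase in Section 11.2, Hypothesis 1 that contrasts EA with ML in this way concerns the correlation with pain, which this trigger does not govern. The point is that the text does not exclude the practice.

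A third reply is that at the pilot effect, the only size of change the documents give for this outcome, the rate is 9%. The larger figures belong to changes of 0.2 to 0.4, chosen to show the range.

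**Conclusion.** The trigger is wrong for its stated purpose under either reading, because a TIME or STIM main effect is not evidence that one arm changed more. The harm is conditional. It is nil if the maps are between-arm contrasts of change (false-positive rate near 5%). If within-arm maps are compared by significance, the joint rates are about 27%, 45%, 41% and 9%, against about 4.5%, 4.8%, 4.4% and 2.1% with an interaction-only trigger.

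The first set should not be read as rates among trials with a significant TIME effect; those are higher at the smaller changes (at 0.3, about 0.45/0.75 = 60%). All the rates assume one summary measure, 40 per arm, two-sided alpha 0.05 for each test (Section 11.2 does not state it) and no dropout. Cluster-corrected maps would give different absolute values.

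The named main test and its 80% power are sound. This should be corrected before analysis, but it does not undermine the design.

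**What to change.** In Section 11.2, Hypothesis 1:

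- Remove the main-effect alternative from the trigger sentence, so that only a significant TIME-by-STIM interaction supports a statement on which arm changed more.
- State that the EA-ML comparison is the between-arm contrast of change.
- Report within-arm pre-post maps as descriptive, without ranking the arms and without inferring a difference from one significant and one non-significant arm.
- Apply the same rule to the paired t-tests in Hypotheses 2 and 3.

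This matches the order already used in Section 11.3, where within-group correlations are explored only after a significant between-therapy map. The cost is a few sentences of text, with no new data, no change in sample size and no loss of power for the interaction.
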